5.7. Restrictions

5.7.1. Fluid and Food Intake

There is no co-administration of food or drink with the study drug. Eating, bowel preparation, and drinking will be held 1 hour before and 1 hour after study drug administration.

5.7.2. Reproduction

Subjects of reproductive capability must agree to use contraception throughout the Follow-Up Period of the study (through Day 30). Acceptable methods include abstinence, intrauterine devices, contraceptive implants, and barrier methods (condom, diaphragm with spermicide).

5.8. Treatment Compliance

Study drug will be administered either by site personnel at the study hospital or by the subject at home prior to surgery. Location for administration is dependent on time of surgery and location for surgical preparation by the subject, and may differ for participating subjects.

5.9. Packaging and Labeling

The Sponsor will provide study materials to the study pharmacy in 120 mL bottles of either active or placebo powder for reconstitution. Glucose powder will be provided in a clearly labeled 60 mL bottle. Reconstitution and labeling instructions are provided in the Pharmacy Manual.

5.10. Study Drug Storage, Preparation, Dispensing, and Accountability

Study drug will be sent to the clinical study site pharmacy. Instructions for requesting additional supplies of product will be provided in the Pharmacy Manual.

Both LB1148 and placebo are to be stored at room temperature. Study drug should be stored carefully at the clinical study site, safely and separately from other drugs. Instructions for the reconstitution of study drug are provided in the Pharmacy Manual.

The site research pharmacist or other authorized site study team personnel will dispense the reconstituted blinded study drug to each subject. The Investigator (or designated pharmacist) will maintain records of:

- The receipt of study drug at the clinical study site;
- The inventory at the site dispensing product to each subject, and
- The return of unused cartons to the Sponsor or destruction at the clinical study site.

During the course of the study, or upon completion or termination of the study, the Investigator/pharmacist will return all unused medication to the Sponsor or destroy all unused medication at the site according to institutional procedures after recording the relevant accountability information. For drug accountability records, the site will provide the Clinical Monitor with a copy of the inventory record and a record of destroyed clinical supplies (on a Drug Accountability Log). The record of destroyed clinical supplies will include information on:

- All dispensed bottles;
- All used and unused bottles returned to the pharmacy;
- All unused bottles;
- All used and unused bottles destroyed in the course of the study;
- Date(s) of destruction, and
- Name and signature of the Investigator/pharmacist.

During and at the end of the study, all study drug will be reconciled against current inventory and the dispensing records as part of routine monitoring visits. After reconciliation, unused (full) bottles will be destroyed at the site per institutional standard operating procedure. At the end of the study, unused, unopened cartons of study drug will be returned or destroyed as instructed by the Sponsor, or its designees.

STUDY PROCEDURES

The schedule of assessments and treatments is provided in [Appendix 1](#). While the subject is in the hospital, all assessments and treatments are to be performed on the study day as indicated.

6.1. Informed Consent

Written informed consent must be obtained from each subject or legal representative designee if subject is unable to sign after the nature of the study has been fully explained in accordance with International Conference on Harmonization (ICH) Good Clinical Practices (GCP). Informed consent must be obtained prior to performing any study-specific procedures.

6.2. Demographics and Medical History

Medical history will include significant medical conditions and surgical history, as well as baseline signs and symptoms occurring within 2 weeks of randomization. Additionally, the subject's diagnosis and reason for requiring a bowel resection will be documented, the planned surgical approach for the bowel resection, the planned use of stoma, and the need for a planned, second surgery. The subject's medical history will be collected during the Screening Period; during this review, a Caprini risk factor score will be calculated ([Appendix 8](#)). Each subject's risk factors for VTE will be assessed in order to determine the appropriate VTE regimen according to each institute's regional antithrombotic guidelines. The subject's prior or current use of tobacco will also be collected.

On the day of the first surgery (the Surgical Period), any changes to subject's condition that affect inclusion/exclusion criteria will be documented. Subject must meet all inclusion/exclusion criteria at time of the first surgery.

6.3. Physical Examination

A complete physical examination (except for genitourinary unless indicated) will be performed at Screening. Height will be measured at the Screening visit only.

From Day 0 through Post-Operative Day 14, and at Hospital Discharge, or study termination, whichever comes first – a brief, focused examination of the subject will be performed, including lower extremity assessments to identify any clinical symptoms of VTE and assessment for AEs. Each focused examination will include weight measurements.

6.4. Surgery Assessment

During surgery (where applicable), the following data should be recorded:

- The type of operation.
- The type of surgical approach (minimally invasive technique or laparotomy).

- The location of the surgical incision(s).
- Surgical time, recorded as:
 - Surgery start time, defined as the time when the initial incision is made, and
 - Surgery end time, defined as when the last suture or staple was placed.
- Ileostomy mobilization time (defined as the time from skin incision to completion of circumferential mobilization and start of preparation of ileostomy for closure).

6.5. Concomitant Medication Assessments

Concomitant medications, including prescription and over-the-counter drugs, will be recorded within 2 weeks prior to randomization through Post-Operative Day 14, and at Hospital Discharge, or study termination, whichever comes first. Additionally, any perioperative surgical preparation that was given or consumed will be documented, including mechanical bowel prep and nutritional supplements (refer to [Section 3.2](#), [Section 5.6](#), and [Section 0](#)).

Blood products administered to the subject will be documented throughout the same timeframe on the Concomitant Medication eCRFs. Documentation will include start and stop dates and reasons for the use.

Unless otherwise specified in the protocol, administration of other concomitant investigational drugs or devices for any indication, other than study drug, is not permitted while on study. Additionally, receiving medication with TXA while taking the study drug is prohibited along with receiving pancreatic enzyme replacement therapy. Any therapeutic or surgical procedures performed during the study period will be documented. Documentation will include information regarding the date(s), indication(s), description of the procedure(s), and/or any clinical or pathological findings.

6.6. Vital Signs

Vital signs will include BP (systolic and diastolic measurements), heart rate (HR), respiratory rate (RR), oxygen saturation, and temperature. Vital signs will be collected daily from Screening through Post-Operative Day 14, and at Hospital Discharge, or study termination, whichever comes first. For study purposes, the vital signs taken the closest to 0800 will be used for data capture.

6.7. Laboratory Tests

6.7.1. Pregnancy Test

A negative urine or serum pregnancy test must be obtained at Screening and confirmed prior to randomization for all females of childbearing potential.

6.7.2. Local Laboratory Tests

Blood samples will be collected during the Screening Period and on Post-Operative Day 3. A lab draw will be performed on Post-Operative Day 7 only if subject is still hospitalized.

[Appendix 2](#) lists the specific laboratory tests that will be performed for this study.

All laboratory evaluations will be conducted at the laboratories located at or associated with the clinical site. Each laboratory will be required to provide up-to-date reference ranges. Laboratory values will be recorded on the eCRF(s).

Unscheduled laboratory results, from tests pre-specified in this protocol, that are both abnormal and clinically significant, as decided by the Investigator, will be recorded on an additional eCRF page(s) and the data will be included in the assessment of out-of-range parameters.

6.8. Study Drug Administration

A total of 700 mL of study drug should be completely consumed orally 2-10 hours prior to induction of surgical anesthesia as a split dose:

- For the first study drug administration, subject will consume 350 mL 6-10 hours prior to surgery.
- For the second study drug administration, subject will consume the remaining 350 mL 2-6 hours prior to surgery.

Eating, bowel preparation, and drinking will be held 1 hour before and 1 hour after study drug administration.

6.9. Perioperative Surgical Preparation

All perioperative items the subject is given or consumed will be recorded during the Screening and Surgical Periods. These include, but are not limited to, mechanical bowel prep, nutritional supplements, carbohydrate drinks, opioids, and analgesia. As indicated in [Section 3.2](#):

- Subjects **must** receive:
 - VTE prophylaxis according to each institute's regional antithrombotic guidelines.
- Subjects **must not** receive:
 - Solid foods consumed for the 8 hours prior to induction of surgical anesthesia;
 - Alternative carbohydrate drinks 8 hours prior to induction of surgical anesthesia; study drug will replace carbohydrate drinks within that time period;
 - Anything by mouth for the 2 hours prior to induction of surgical anesthesia (exception: daily oral medication such as anti-hypertensive may be taken with small volume of water as directed by physician), and

Additional information concerning restrictions are provided in [Section 5.7](#).

6.10. Taste Assessment

In the first phase of the study, after the study drug has been consumed and before surgical anesthesia is administered during the Surgical Period, subject satisfaction with the taste of the study drug will be recorded.

6.11. Opioid Use

The use of opioid pain medications will be collected daily from Screening through Day 14, and at Hospital Discharge or study termination, whichever comes first.

6.12. Pain Assessment

The NPRS is an 11-point scale used to evaluate pain based on subject feedback. This scale can be administered either verbally or graphically by the clinician where subjects are asked to rate their current pain intensity from 0 (“no pain”) to 10 (“worst possible pain imaginable”). The NPRS is the method recommended by both the Initiative on Methods, Measurement and Pain Assessment in Clinical Trials as well as the Expert Working Group for the assessment of pain intensity during a clinical study ([Breivik et al., 2008](#); [Caraceni et al., 2002](#)). A change of approximately 30% (or 2 points) has been shown to represent a clinically meaningful change in pain ([Farrar et al., 2001](#)).

Investigator or delegated site personnel should use the following statements to ask the subject to rate their post-operative abdominal pain:

1. I would like you to rate your pain on a scale from 0 to 10.
2. ‘0’ means you have no pain at all.
3. ‘10’ means the worst possible pain you can imagine.
4. What number would you give to your pain?

A pain assessment will be collected daily starting after Surgery Day 0 through Day 14, and at Hospital Discharge, or study termination, whichever comes first ([Appendix 4](#)).

6.13. Gastrointestinal Function Assessment

Starting on Post-Operative Day 1, GI function will be assessed to determine return of GI function. Daily GI assessments will be collected until either the subject has had return of GI function or Hospital Discharge. If, while still in the hospital, GI function deteriorates to the point of no longer being able to tolerate an oral diet and pass stool, daily measurements should be collected again until the subject has had return of GI function.

Data for this assessment will include but not be limited to:

- Nausea and vomiting (either subject reported or recorded as presence or absence, date and time, including VRS [[Appendix 3](#)]),
- Passing of flatus (either subject reported or Investigator/delegated site personnel reported during a 24-hour calendar day; date and time of first flatus where only the first observance is recorded; in any instance where subject has post-operative complications and experiences ileus as decided by Investigator, the next flatus event should be recorded);
- Passing of stool from anus or ostomy (recorded as presence or absence and date and time);
- Presence of NG/OG tube (including date and time).
- Ability to tolerate liquid diet (liquid diet ordered, subject is able to sustain oral liquid intake without need for IV fluid administration, and total liquid volume over a 24-hour calendar day);
- Ability to tolerate a solid diet (solid diet ordered and date and time of solid food ingestion without significant nausea or vomiting for 4 hours).
- If a subject experiences a POI event during hospitalization, this event will be recorded, including date and time as an AE/SAE.

6.14. Hospital Discharge

Subjects may not be discharged until all of the following criteria are met:

- Passage of stool
- Ability to tolerate solid food and drink comfortably
- Adequate oral analgesia
- Subject's willingness to be discharged.

Information related to Hospital Discharge after the first bowel resection will be recorded during the Post-Surgical period as:

- When discharge order is written (date and time)
- When subject departs from the hospital (date and time)

6.15. Day 30 Follow-Up

On Day 30 (+7 days), site study staff will contact the subject or their legally authorized representative to determine if the subject experienced a hospital readmission due to GI concerns and/or other medical reasons. If readmission did occur, this event should be recorded as a SAE.

As it is vital to obtain follow-up data, every effort must be made to contact the subject or legally authorized representative to collect this information.

6.16. Adhesions Assessment (Day 0 and at time of second surgery)

The surgeon will determine the incidence, extent, and severity of adhesions at the time of surgical closure for the first surgery and at the time of opening for the second surgery. Grading of the adhesions (extent and severity) will be performed by the surgeon during the surgical procedure ([Appendix 5](#)).

For each abdominal region, the score of the extent and severity of adhesions are evaluated. The surgeon will grade the intra-abdominal adhesions at 9 abdominal region (right upper, epigastrium, left upper, left flank, left lower, pelvis, right lower, right flank and central) and when appropriate at 4 areas around the ostomy (superior, lateral, inferior, and medial). ([Coccolini et al., 2013](#), [Dabrowski et al., 2016](#), and the [Seprafilm Package Insert](#)).

For each abdominal region, extent of adhesion formation is scored for adhesions from the abdominal wall to bowel (including abdominal wall to viscera) and for adhesions from bowel to bowel (including bowel to viscera) as follows:

- 0 = no adhesion;
- 1 = minimal (<1/3 of the site is covered);
- 2 = moderate (1/3 to 2/3 of the site is covered), or
- 3 = extensive (>2/3 of the site is covered).

The severity of the adhesions in the region are graded using the following score:

- 0 = no adhesions;
- 1 = filmy thickness, avascular;
- 2 = moderate thickness, limited vascularity, or
- 3 = dense thickness, vascularized.

At the second surgery visit the site study staff will determine if the subject experienced a hospital readmission due to GI concerns and/or other medical reasons. If readmission did occur, this event should be recorded as a SAE.

6.17. Appropriateness of Measurements

All procedures used to measure the safety and efficacy of LB1148 in this study are considered to be appropriate and necessary to obtain the required safety, tolerability, and efficacy data. The safety assessments used in this study, such as physical examination, vital signs, opioid use, laboratory assessments, and GI function assessments are widely used and are considered appropriate for monitoring subjects' health and well-being in this type of study. The measure used to evaluate pain levels is a validated and widely accepted rating scale used for clinical studies evaluating pain.

ADVERSE EVENTS ASSESSMENTS

AE data will be collected from first administration of study drug through Day 14, Hospital Discharge, or study termination, whichever comes first. Following discharge through the second surgery visit, any hospital readmissions will be recorded as SAEs.

AEs/SAEs related to the second surgery will also be collected.

Investigators are responsible for monitoring the safety of subjects who have entered this study and for alerting the Sponsor or its designees to any event that seems unusual, even if this event may be considered an unanticipated benefit to the subject.

The Investigator is responsible for the appropriate medical care of subjects during the study. The Investigator remains responsible for following, through an appropriate health care option, SAEs or AEs that caused the subject to discontinue before completing the study. The subject should be followed until the event is resolved or explained. Frequency of follow-up evaluation is left to the discretion of the Investigator.

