1.2. Post-Operative Ileus

All patients undergoing bowel resection experience some degree of post-operative ileus (POI), a transient cessation of bowel motility. Prolonged POI is a serious complication of abdominal surgery, resulting in increased morbidity, hospital length of stay, and costs. Post-surgical hospital stays for patients who develop POI are 4-6 days longer than for patients who do not develop POI, resulting in a major burden on patients and health care providers each year (Berger et al., 2015; Goldstein et al., 2007; Iyer et al., 2009; Jakobsen et al., 2014).

Although POI is common after abdominal surgery, there is no widely agreed upon definition in the literature. The [2006 Clinical Consensus](#) defines POI as “transient cessation of coordinated bowel motility after surgical intervention, which prevents effective transit of intestinal contents or tolerance of oral intake”. The 2006 Clinical Consensus defines primary POI as occurring in the absence of any precipitating complication, whereas secondary POI occurs in the presence of a precipitation complication (bowel obstruction, infection, etc.). The 2006 Clinical Consensus also defined 3 types of POI:

1. Panintestinal ileus (no flatus or bowel movement, presence of nausea and vomiting);
2. Upper GI symptoms (nausea, vomiting and flatus present), and
3. Lower GI (no flatus or bowel movement, tolerance of diet).

The mechanism of POI remains elusive and is likely multifactorial, involving the central nervous system (CNS, specifically the autonomic nervous system), inflammation (mast cell inflammatory process), the enteric nervous system, hormones, neuropeptides, anesthesia, narcotics and digestive enzymes ([2006 Clinical Consensus](#); Gan et al., 2015; Iyer et al., 2009; Jakobsen et al., 2014; Kalff et al., 1998; Kraft et al., 2010; Ludwig et al., 2008; Vather et al., 2013; Vather et al., 2014; Vather et al., 2015; Wolthius et al., 2016).

POI prevention strategies include the type of opioid ([Gan et al., 2015](#); Berger et al., 2015) and anesthesia used ([Goldstein et al., 2007](#)). Nursing prevention strategies include early patient ambulation, early introduction of a peroral diet, selective use of a NG tube, and the use of non-opioid analgesics ([2006 Clinical Consensus](#)). Additionally, Entereg® (alvimepant) has been approved for use in the US as a gut motility stimulator to restore gut function after surgery.

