1.4. Rationale for Use of LB1148

The intestinal mucosal barrier plays a key role in both acute critical care medical conditions as well as burdensome chronic diseases. Healthy maintenance of the intestinal mucosal barrier requires oxygenation and blood flow and avoidance of mechanical or physical injury. Potent digestive enzymes are maintained within the intestine as long as normal blood flow continues and no damage or disturbances to the wall occur.

Breakdown of the intestinal mucosal barrier can be produced by wide variety of events. These include prolonged low blood pressure ([BP] e.g. during shock), disruption of blood flow (e.g. during ischemia), and physical and mechanical perturbations (e.g. during trauma or abdominal surgery).

One of the key advances toward the use of LB1148 to reduce post-operative complications was the learning that with more subtle perturbations of the mucosal barriers, such as during abdominal surgery, intraluminal pancreatic digestive enzymes played a role in the pathology of GI dysfunction. When the mucosal barrier was disturbed, the pancreatic digestive enzymes had a profound effect on the tissue the enzymes contacted first, namely, the intestine. Importantly, the enterotomy into the bowel during resection and anastomosis is sufficient to release pancreatic digestive enzymes, which delays the return of gut function. Perioperative enteral administration of LB1148 in preclinical models was sufficient to reduce the delayed return of GI function. Furthermore, the reduction in pancreatic digestive enzyme-induced tissue damage had a profound reduction in post-operative adhesion formation. Together, these preclinical studies provide evidence that blocking pancreatic digestive enzymes with LB1148 in the intestinal lumen reduces local tissue damage, preserves GI function, and reduces adhesion formation.

LB1148 was designed to stop the downstream effects of a disruption of the intestinal mucosal barrier by inhibiting digestive enzymes only in the lumen of the bowel and not systemically. One of the objectives of this study is to determine if a single split dose of LB1148 reduces the mucosal barrier breakdown and the leakage of digestive enzymes, thereby preventing local tissue damage and ultimately decreasing the number of hours from surgical closure to return of normal GI function.

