2.1.2. Secondary Objectives

The secondary objectives of this study are to determine the following among subjects treated with LB1148 or placebo:

- Compare time from surgical closure to resolution or appearance, as appropriate, of 1 or more of the components common to gastrointestinal (GI) dysfunction following elective bowel resection with a planned stoma.
- Compare number of hours to GI2.
- Compare number of hours to GI3.
- Compare number of hours to resolution of POI.
- Compare hospital length of stay (LOS, recorded in hours) through Discharge or Day 14 (whichever comes first).
- Compare the incidence of intra-abdominal adhesions following the second surgery among subjects treated with LB1148 or placebo.
- Compare the extent and severity of intra-abdominal adhesions following the second surgery among subjects treated with LB1148 or placebo.
- Compare change from baseline in incidence, extent, and severity of intra-abdominal adhesions among subjects treated with LB1148 or placebo who had adhesions observed at the time of the first surgery.
- Assess the safety and tolerability of LB1148 in subjects undergoing elective bowel resection.

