3.1. Overall Study Design and Plan

This is a multicenter, randomized, double-blind, parallel, placebo-controlled, proof-of-concept, adaptive design, Phase 2 study to evaluate LB1148 for return of GI function, reduction of POI and intra-abdominal adhesions in subjects undergoing elective bowel resection with a planned stoma.

Figure 1 Illustration of Study Design for Protocol LBS-POI-201

* Study Day 0 is the day of surgery. Study dosing could occur on Day -1 and/or up to 2 hours prior to surgery on Day 0.

Subjects scheduled for elective bowel resection, aged 18 to 80 years inclusive, will be screened within 42 days of randomization (Study Day -1). Subjects who meet all inclusion and no exclusion criteria, and provide written informed consent, will be stratified by: 1) surgical approach (either minimally invasive technique or laparotomy) and 2) with or without a planned stoma, and then randomized to receive a split oral liquid dose of LB1148 or placebo (polyethylene glycol [PEG], glucose, and electrolytes) in a 1:1 ratio.

All subjects will receive 350 mL of study drug 6-10 and 2-6 hours prior to surgery (Study Day 1/2). Subjects will then undergo the first surgery. At the time of surgical closure, the investigator will determine the incidence, extent, and severity of adhesions using the Intra-Abdominal Adhesion Extent and Severity Assessment Worksheet ([Appendix 5](#)).

Subjects will be assessed for safety and tolerability, including AEs, physical exam, vital signs, clinical lab tests (chemistry, coagulation, and hematology) while in the hospital and on Day 30. Subjects will be monitored for return of bowel function while in the hospital and discharged following tolerance of solid food and first bowel movement.

Within 8 months of enrollment, subjects will undergo a second surgery for the purpose of ostomy take down or other planned abdominal surgery, at which time the surgeon will determine the incidence, extent, and severity of adhesions. If a subject is not ready for the second surgery by 8 months, the investigator may consult with Medical Monitor to obtain window approval.

Unless required for safety reasons or protocol compliance, all subjects, Investigators, and study site personnel will remain blinded to the identity of the treatment from time of randomization until final database lock.

The Schedule of Assessments is provided in [Appendix 1](#) and the study endpoints are in [Section 2.2](#).

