7.6. Post-Surgical Complications

The impact of study drug on LOS is a secondary endpoint for this study. As such, any post-surgical complication that prolongs discharge will be recorded as an AE/SAE.

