12 SAFETY ANALYSIS

12.1 Adverse Events

All adverse events will be coded using the Medical Dictionary for Regulatory Activities (MedDRA) coding system (Version 25.0). Frequency tables will be presented by treatment group for all adverse events (AEs) by system organ class and preferred term for the safety population. Frequency tables will also be presented for AEs leading to discontinuation of test article, AEs by maximum severity (per CTCAE Version 5.0 Section 7.11 Study Protocol), AEs related to test article, and serious AEs. Subject listings of all AEs will also be provided for the safety population.

In all displays, adverse events will be displayed by MedDRA System Organ Class (SOC) and Preferred Terms. Subjects who have the same AE occur more than once will be counted only once for that event. Subjects who have more than one AE within a system organ class will be counted only once in that system organ class. (The addition of severity or relatedness follow the same pattern.)

In addition, frequency tables by treatment group for all AEs by system organ class and preferred term will be presented for the following populations:

- Patients who have had chemotherapy in the last 60 days
- Patients with a venous port or catheter
- Patients with varicose veins and superficial vein thrombosis
- Patients with varying degrees of obesity
 - Baseline BMI 30-35
 - Baseline BMI 35-40
- Patients who are smokers
- Patients with varying degrees of renal function

- Baseline eGFR 45-59
- Baseline eGFR 30-44
- Baseline eGFR 15-29
- Baseline eGFR < 15
- Patient age groups
 - 18-64 years
 - 65-80 years

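### General AE collection stops at hospital discharge, so the AE tables rest on unequal observation time if length of stay differs between arms

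*Protocol*

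**What the plan says.** **AE window.** Protocol Section 7 (opening text) and 7.9 both state: "AE data will be collected from first administration of study drug through Day 14, Hospital Discharge, or study termination, whichever comes first". For any subject discharged before Day 14, general collection ends at discharge.

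**Discharge as an outcome.** Protocol 7.6 states: "The impact of study drug on LOS is a secondary endpoint for this study". Length of stay is a secondary objective in Protocol 2.1.2 and SAP 3.2, and is analysed by arm under SAP 11.3. Protocol 1.4 gives the intended effect as "ultimately decreasing the number of hours from surgical closure to return of normal GI function". Protocol 3.1 says subjects will be "discharged following tolerance of solid food and first bowel movement", and 6.14 makes passage of stool and tolerance of solid food conditions of discharge.

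**Analysis.** SAP 12.1: "Frequency tables will be presented by treatment group for all adverse events (AEs) by system organ class and preferred term for the safety population". A subject is counted once per event. SAP Section 12 describes no common window, no person-time and no display of observation days.

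**What continues after discharge.**
- Readmissions are recorded as SAEs, to the second surgery visit (Section 7) or to Month 3 (7.9).
- Ileus before Day 30 is recorded (7.5).
- Known later events that the investigator judges drug-related are reported (7.9).
- Events related to the second surgery are collected.
- Section 7.4 says thrombotic events are recorded and followed to resolution, but sets no window of its own.
- The Day 30 contact is a telephone call about readmission and vital status, and only readmissions are to be recorded from it (6.15; Appendix 1, footnote 13).

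**The concern.** The end of AE observation is set by something the treatment may change. If one arm goes home sooner, its subjects have fewer days in which an AE can be recorded, and crude counts per arm do not show this. Complications that delay discharge also lengthen the window. A difference in the tables would then mix a real effect with a window effect, and the tables could not separate the two.

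Safety and tolerability is a stated secondary objective, and thrombotic events are of special interest (7.3). The lower-extremity examinations for venous thromboembolism also stop at Day 14 or discharge (6.3), and SAP 12.3 tabulates their findings by arm. A thrombosis that appears after discharge and is managed without readmission has no scheduled contact designed to find it.

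**Working it through.** **No planned figure to reproduce.** The documents state no AE rate, expected stay by arm, or effect size (Protocol 9.2; SAP 4.3). All stays and hazards below are assumptions.

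**Set-up.** Both arms have the same true AE process. L is the days observed to discharge, below the Day 14 cap. Only L differs.
- Constant hazard h per day: recorded share = 1 − exp(−h·L)
- Front-loaded hazard, with cumulative hazard H to Day 14: recorded share = 1 − exp(−H·√(L/14))

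**One day shorter on LB1148 (5 v 6 days).** Differences and ratios are from unrounded values.

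| Hazard | LB1148, L = 5 | Placebo, L = 6 | Difference (points) | Risk ratio |
|---|---|---|---|---|
| constant, h = 0.05 | 22.1% | 25.9% | 3.8 | 0.853 |
| constant, h = 0.10 | 39.3% | 45.1% | 5.8 | 0.872 |
| constant, h = 0.20 | 63.2% | 69.9% | 6.7 | 0.905 |
| front-loaded, H = 0.5 | 25.8% | 27.9% | 2.1 | 0.925 |
| front-loaded, H = 1.0 | 45.0% | 48.0% | 3.1 | 0.937 |
| front-loaded, H = 2.0 | 69.7% | 73.0% | 3.3 | 0.955 |

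For example, with h = 0.10: 1 − e^(−0.5) = 39.3% and 1 − e^(−0.6) = 45.1%.

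**Two days shorter (4 v 6 days).** The risk ratio is 0.699, 0.731 and 0.788 for the three constant hazards, and 0.840, 0.862 and 0.900 for the three front-loaded ones.

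**Equal stays (6 v 6 days).** The risk ratio is 1.00 in every case.

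**Using the protocol's ileus figure.** Protocol 1.2 states: "Post-surgical hospital stays for patients who develop POI are 4-6 days longer than for patients who do not develop POI". This contrasts patients with and without ileus, so it needs an assumed ileus difference between arms. Assume a base stay of 5 days, ileus in 25% on placebo and 10% or 15% on LB1148, and h = 0.10.
- Excess of 4 days: mean stay 5 + 0.25×4 = 6.0 on placebo; 5.4 or 5.6 on LB1148. Risk ratio 0.932 or 0.955.
- Excess of 6 days: mean stay 5 + 0.25×6 = 6.5 on placebo; 5.6 or 5.9 on LB1148. Risk ratio 0.911 or 0.941.

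The mean difference between arms is then 0.4 to 0.9 days, not 4 to 6.

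**Common window.** With collection to Day 14 in both arms and h = 0.10, the share is 1 − e^(−1.4) = 75.3% in each arm, so the ratio is 1.00.

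**Do person-day rates repair it?** Only under a constant hazard. Under the front-loaded form the cumulative hazard grows as √L, so the rate per observed day is proportional to √L/L = 1/√L. For 5 v 6 days the rate ratio is √(6/5) ≈ 1.10: a spurious excess on LB1148 with no true difference.

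**The case against.** Much of the case on the other side stands.

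**A reader might infer that LB1148 will look safer.** The documents do not support that unconditionally. They assume no effect on stay. Discharge also requires adequate oral analgesia and the subject's willingness (6.14), and SAP 4.1 records that COVID-19 led to some pre-2022 discharges before GI2. With equal stays there is no bias, and with a longer stay on LB1148 it runs the other way.

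**A reader might infer that thrombotic events after discharge are never counted.** That goes too far. Section 7.4 sets no discharge limit. Section 7.9 takes in known later events judged related. Section 7.13 has SAEs reported irrespective of relationship, with Month 3 among its stated end points, and under 7.2 an SAE need not involve hospitalization. Readmissions and ileus before Day 30 are captured, so the SAE and ileus results are better protected. What remains is that the 7.9 route is passive and the Day 30 call records readmissions only: other events are not actively solicited.

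**The tables are descriptive.** SAP 12.1 names no test, the safety objective is to assess rather than compare, and the trial is an unpowered proof-of-concept study. This lowers the stakes but does not make the counts comparable, because they are laid out by arm and will be read that way.

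**A constant hazard is the less favourable assumption.** Study drug is taken only in the 10 hours before surgery, so a front-loaded hazard is plausible, and it gives the smaller distortion.

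**Conclusion.** The concern holds in conditional form. The AE window ends at an outcome that the drug is intended to change, and the planned tables neither equalise nor display observation time. If stays differ, ascertainment favours the arm discharged sooner. For an assumed one-day difference (5 v 6 days) the spurious risk ratio is 0.853 to 0.905 under a constant hazard and 0.925 to 0.955 under a front-loaded one. A two-day difference (4 v 6 days) roughly doubles the distortion. All of this rests on assumed stays and hazards.

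The exposure is mainly AEs that do not lead to readmission, including thrombotic events managed as outpatient. The ileus figure in Protocol 1.2 should not be read as a difference in stay between arms. Person-day rates should not be taken as a correction: they can reverse the bias, and discharge is informative about a subject's condition. The change is worth making because it is cheap and the AE tables are the main answer to the safety objective.

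**What to change.** 1. **Protocol 7, 7.9 and Appendix 1 footnote 13.** Give general AE collection one common end for every dosed subject regardless of discharge, for example Day 14, or Day 30 to match the existing call. Ask about AEs, including thrombotic events, at that call. Cost: a sentence in two sections, a footnote, and a few questions at a contact already scheduled. The downside is less precise recall. The call falls on Day 30 (+7), so an event on Day 14 is 16 to 23 days back (30 − 14 and 37 − 14), and earlier events are further back.

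2. **SAP 12.1, for data already collected.** Show AE-observation days by arm, and label crude AE counts as in-hospital with unequal follow-up. Any person-day rate should be supplementary, with a stated caution about front-loaded hazard and informative discharge. Cost: one summary row and a table footnote. This step remains possible if enrolment has finished.

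3. **Reconcile the reporting periods.** Post-discharge reporting ends at the second surgery visit in Section 7 but at Month 3 in 7.9. Section 7.13 lists discharge, Month 3 or early termination without saying which governs. Ileus is recorded to Day 30 in 7.5, while the Day 30 call is limited to readmissions. Separately, Protocol 3.1 describes safety assessment including "clinical lab tests (chemistry, coagulation, and hematology) while in the hospital and on Day 30", but Appendix 1 schedules no laboratory test or examination at Day 30. The last is a documentary conflict and does not bear on the size of the bias.
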